6.7.2.2.5 Definition of Serious Adverse Events

A **serious adverse event (SAE)** is any adverse drug experience occurring at any dose and any study phase (e.g., treatment, follow-up) that results in any of the following outcomes (as determined by either the investigator or sponsor):

- death;
- life-threatening AE (i.e., one that places the subject, in the view of the investigator or sponsor, at immediate risk of death from the AE as it occurs; it does not include an adverse event that, had it occurred in a more severe form, might have caused death);
- requires in-patient hospitalization (i.e., admission) or prolongs existing hospitalization (for ≥ 24 hours);
- persistent or significant disability/incapacity (i.e., substantial disruption of the ability to conduct normal life functions);
- congenital anomaly or birth defect;
- an important medical event that may not result in death, be life-threatening,

or require hospitalization may be considered a serious adverse event when, based upon appropriate medical judgment, they may jeopardize the subject and may require medical or surgical intervention to prevent one of the outcomes listed in this definition. Examples of such medical events include allergic bronchospasm requiring intensive treatment in an emergency room or at home, blood dyscrasias, or convulsions that do not result in in-patient hospitalization, or the development of drug dependency or drug abuse.

In addition to the general definitions above for SAEs, **the following specific events will be considered as SAEs** in the context of this study:

- Anaphylaxis: defined as \geq CTCAE Grade 3 or meeting Sampson criteria (**Appendix C**);
- Decrease from Baseline in platelet count to a value $<50,000/\text{mm}^3$ (=CTC Grade 3)

Clarification should be made between the terms “serious” and “severe” since they are not synonymous. The term “severe” is often used to describe the intensity (and defined by the grading/severity scale) of a specific event (as in mild, moderate, or severe pain); the event itself, however, may be of relatively minor medical significance. This is NOT the same as “serious,” which is based on the strict definition listed above and is based on subject or event outcome or action criteria usually associated with events that pose a threat to a subject’s life or functioning. A severe AE does not necessarily need to be considered serious. Investigators should assess adverse event severity and seriousness independently.

Since the criteria for CTCAE severity differs from the regulatory criteria for serious adverse events, if adverse events correspond to grade 4 “life-threatening” CTCAE severity criteria (e.g., laboratory abnormality reported as grade 4 without manifestation of life-threatening status), it will be left to the investigator’s judgment to also report these abnormalities as serious adverse events. For any adverse event that applies to this situation, comprehensive documentation of the event’s severity status must be recorded in the subject’s medical record.

All SAEs, whether or not deemed study drug-related or expected, **must be reported** by the investigator or qualified designee to the sponsor **within 24 hours of first becoming aware of the event**. The investigator/qualified designee will enter the required information about the SAE into the appropriate module of the eCRF, which will automatically result in distribution of the information to the appropriate sponsor contact(s). If the eCRF system is temporarily unavailable, then a full description of the event and any sequelae should be provided as a telefacsimile (FAX). If both the eCRF and FAX are not available, the event should be reported by telephone.

SAE Reporting Contact Information

If the report is initially given to the sponsor via telephone, a full description of the event and any sequelae, including the investigator-determined causality to study drug must be provided in writing (by FAX or eCRF) as soon as possible, so that the appropriate written report can be completed by the sponsor. If the report is initially given by FAX or telephone, then the required information about the SAE will be entered into the appropriate module of the eCRF immediately after the eCRF system is available.

The investigator is responsible for ensuring that all SAEs that occur at any time after the subject has been randomized up through 90 days following the study drug administration are reported to the sponsor. New information relating to a previously reported SAE must be submitted to the sponsor within 24 hours of receipt. The investigator may be asked to provide additional follow-up information, which may include a discharge summary or extracts from the medical record. Information provided about the SAE must be consistent with that recorded on the applicable eCRF.

Any SAE (including those which are ongoing when a subject completes his/her participation in the trial) must be followed by the site investigator (and will be followed by the sponsor) until one of the following occurs:

- the event resolves or stabilizes; or
- the event returns to baseline condition or value (if a baseline value is available).

Events which are ongoing at the time the clinical database is closed will be recorded as unresolved.

Reports of all SAEs must be communicated as soon as possible by the investigator to the appropriate IRB and/or reported in accordance with local law and regulations.

Federal regulations require that the sponsor, Tufts Medical Center, to report any suspected adverse reactions (“reasonable possibility” that the drug caused the event) that are both serious and unexpected (21 CFR 312.32). Such events must be reported to the Food and Drug Administration (FDA), the NHLBI/NIH and all participating investigators (i.e., all investigators to whom the sponsor is providing drug under its IND) within 15 calendar days after the sponsor receives the information and determines that it qualifies for reporting. Such notification must occur within 7 calendar days if the serious unexpected suspected adverse reaction (SUSAR) was fatal or life-threatening. The sponsor is also required to report other serious adverse events and qualifying adverse events in an expedited manner to its IRB in

compliance with local institutional and IRB policies. Therefore, once the investigator has determined that an SAE has occurred, it is important to adhere to the reporting timeframes outlined above. After receiving the investigator's SAE report, including the investigator's assessment of causality, the sponsor will also assess the event for seriousness and the relationship to PZ-128/Placebo, and will determine if the event was unexpected.

Investigational New Drug Safety Reports (INDSRs) will be reported to the FDA and NHLBI/NIH by Tufts Medical Center and copies of the report(s) will be distributed to all participating clinical investigators. The investigator is responsible for notifying the relevant IRB of all INDSRs in accordance with institutional and IRB policies in addition to any other safety information which has been provided by the sponsor throughout the duration of the trial.

To comply with reporting regulations for serious adverse events, the treatment assignment of subjects who develop serious, unexpected, and related adverse events may be unblinded by the sponsor before submission to regulatory authorities.

6.7.2.2.6 Reporting of Subject Death

The **death of any subject** after enrollment/randomization up through 90 days following the study drug administration, regardless of the cause, **must be reported** by the investigator or qualified designee to the sponsor **within 24 hours of first becoming aware of the death**. If the report is given to the sponsor via telephone rather than in writing on the form designated for SAE reporting, a full description of the event and any sequelae, including the investigator-determined causality to study drug must be provided, so that the appropriate written report can be completed by the sponsor. If an autopsy is performed, the report must be provided to the sponsor. Reports of all deaths must be communicated as soon as possible to the appropriate IRB and/or reported in accordance with local law and regulations.

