6.7.2.2.10 Protocol-Specific Exceptions to SAE Reporting to Sponsor

Suspected clinical endpoint events that are also serious adverse events are to be recorded in the subject's eCRF (bleeding or clinical efficacy endpoint modules), but will **not** be reported in an expedited manner to the sponsor's SAE contact as serious adverse events. The suspected endpoint events recorded in the eCRF will be monitored in aggregate by the DSMB at appropriate intervals in order to detect any potential imbalance between the study arms which would suggest that the events are occurring more frequently or at higher severity in the study drug treatment group than the control group.

Specifically, the following events will **not** be reported in an expedited manner to the sponsor's SAE contact:

- activity/efficacy endpoints- MACE- any of cardiovascular death, non-fatal MI, non-fatal stroke, recurrent ischemia requiring hospitalization, or urgent coronary revascularization with PCI or CABG; and stent thrombosis
- safety endpoints- any bleeding that does **not** result in death, regardless of severity

Note that death unrelated to cardiovascular disease and death attributable to bleeding **will** be reported in an expedited manner to the sponsor's SAE contact.

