Cardiovascular death is the endpoint defined in this trial (as opposed to all-cause death) and only suspected CV death cases will be submitted for adjudication to the CEC. Death will be classified as cardiovascular, non-cardiovascular, or unknown/undetermined. All deaths will be assumed to be cardiovascular in nature unless a non-cardiovascular cause can be clearly shown, with the exception of death without any additional information, which will be classified as unknown/undetermined.

The primary cause of death is determined by the principal condition that caused the death, not the immediate mode of death, as per the following:

Cardiovascular death:

- **Acute MI**

Death by any cardiovascular mechanism (arrhythmia, sudden death, HF, stroke, pulmonary embolus, PAD) within 30 days after an acute MI, related to the immediate consequences of the MI, such as progressive HF or recalcitrant arrhythmia. There may be assessable (attributable) mechanisms of cardiovascular death during this time period, but for simplicity, if the cardiovascular death occurs within 30 d of an acute MI, it will be considered a death due to MI.

Note: Acute MI should be verified to the extent possible by the diagnostic criteria outlined for acute MI or by autopsy findings showing recent MI or recent coronary thrombosis. Death resulting from a procedure to treat an MI (PCI or CABG), or to treat a complication resulting from an elective coronary procedure to treat myocardial ischemia (i.e., chronic stable angina) or death due to an MI that occurs as a direct consequence of a cardiovascular investigation/procedure/operation should be considered as a death due to a cardiovascular procedure.

- **Sudden cardiac death**

Death that occurs unexpectedly and not within 30 d of an acute MI.

Note: Sudden cardiac death includes the following scenarios:

- Death witnessed and occurring without new or worsening symptoms;
- Death witnessed within 60 min of the onset of new or worsening cardiac symptoms unless the symptoms suggest acute MI;
- Death witnessed and attributed to an identified arrhythmia (e.g., captured on an ECG recording, witnessed on a monitor, or unwitnessed but found on ICD review);
- Death after unsuccessful resuscitation from cardiac arrest (e.g., ICD unresponsive sudden cardiac death, pulseless electrical activity arrest);
- Death after successful resuscitation from cardiac arrest and without identification of a specific cardiac or noncardiac etiology;

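### Sections 6.7.2.2.6 and 6.7.2.2.10 give opposite rules for reporting a non-bleeding cardiovascular death to the sponsor, and nothing says which governs

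*Combined protocol and SAP*

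**What the plan says.** Section 6.7.2.2.6 deals only with deaths. Any subject's death "after enrollment/randomization up through 90 days following the study drug administration, regardless of the cause" must be reported to the sponsor "within 24 hours of first becoming aware of the death". The section expects the report either by telephone or "in writing on the form designated for SAE reporting", and asks for the investigator's view of causality. It separately requires deaths to be communicated to the IRB as soon as possible.

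Section 6.7.2.2.5 sets the general rule. Death is an SAE outcome, and SAEs are due "within 24 hours of first becoming aware of the event". Entry in the SAE module automatically alerts the sponsor's contacts.

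Section 6.7.2.2.10 is headed as a set of exceptions to SAE reporting to the sponsor. It applies to suspected endpoint events. Its list of events left out of expedited reporting begins "activity/efficacy endpoints- MACE- any of cardiovascular death, non-fatal MI, non-fatal stroke". A closing note keeps expedited reporting for "death unrelated to cardiovascular disease and death attributable to bleeding". The exempt events go into the eCRF endpoint modules and are followed in aggregate by the DSMB. Section 6.6.1 repeats the exemption for MACE, including cardiovascular death, and refers the reader to Section 6.7.2.2.10.

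**The concern.** For one class of death, a site cannot tell from the protocol what it owes the sponsor. One section demands notice within a day whatever the cause; the other makes the duty depend on the cause and removes it for cardiovascular death. With three sites, the same death could be handled in different ways.

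What is at stake is how soon the sponsor's own assessment begins. Under Section 6.7.2.2.5 the sponsor judges seriousness, relatedness and expectedness after receiving the investigator's SAE report, and a fatal unexpected suspected reaction must be notified within 7 calendar days. A death that bypasses the SAE contact may enter that process late. This matters for PZ-128 because Section 4.2.1 records anaphylactoid/histaminic reactions at 1-2 mg/kg in phase 1, and the 2-hour infusion, which starts no more than an hour before catheterization, overlaps the procedure. A drug reaction could at first be taken for a cardiac event, and the exception works on the suspected event rather than the adjudicated one.

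**Working it through.** There is no figure in the plan to reproduce and no arithmetic to do. The check sets the rules side by side for each kind of death.

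| Kind of death | Section 6.7.2.2.6 | Section 6.7.2.2.10 | Result |
|---|---|---|---|
| Non-cardiovascular, cause known | 24 hours | Expedited | Agree |
| Attributable to bleeding, not cardiovascular | 24 hours | Expedited | Agree |
| Cardiovascular, not bleeding | 24 hours | Exempt | Conflict |
| Cardiovascular hemorrhage (Appendix B) | 24 hours | Exempt as cardiovascular, expedited as bleeding | Ambiguous |
| Unknown or undetermined cause | 24 hours | Not assigned | Gap |

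1. The third row is the direct contradiction. Section 6.7.2.2.6 says the cause does not matter; Section 6.7.2.2.10 makes the cause decisive.

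2. The fourth row arises because Appendix B counts certain hemorrhagic deaths, such as tamponade or a subdural hematoma, as cardiovascular. They meet both the exempt and the expedited description.

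3. The fifth row arises because Appendix B has a third class of death, unknown or undetermined, which Section 6.7.2.2.10 never mentions.

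4. Nothing settles precedence. Neither of the two sections cites the other. Each is specific in its own way, one to deaths and one to endpoint events, so the usual presumption that the specific rule prevails does not decide the matter.

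5. The route left under the exception is slower on paper. The documents describe no automatic alert and no hour limit for the endpoint module. Section 8.2 asks only that eCRF screens be completed soon after the evaluation. The DSMB sees the data in aggregate, blinded by default, quarterly or as required (Section 9.3.1).

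**The case against.** The best reply is that the two sections describe different channels. Section 6.7.2.2.6 speaks of the sponsor and accepts a telephone call; Section 6.7.2.2.10 speaks of the sponsor's SAE contact. A site could telephone the sponsor about every death and still not file a cardiovascular death as an expedited SAE. That reading is possible but weak. The death section itself points to the SAE form and asks for causality, the exception's own heading concerns SAE reporting to the sponsor, and no other 24-hour route is described. If two channels were meant, the text has to say so.

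Several stronger readings are tempting, and the documents do not support them:

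- A reader might infer that a fatal infusion reaction would go unreported. Anaphylaxis is a named SAE in its own right (Section 6.7.2.2.5), death from a drug reaction is classed as non-cardiovascular (Appendix B) and so stays expedited, and medical staff must be present during the infusion (Section 6.4.7.7). What remains is a reaction first misread as cardiac.
- A reader might infer a delay of up to three months from the quarterly DSMB meetings. That is not the real alternative. eCRF entry is due soon after the evaluation, the CEC adjudicates on a rolling basis (Section 6.1), the IRB must still be told of every death, and the DSMB can meet or call a review at any time.
- A reader might infer that the exception covers most deaths, because Appendix B says "All deaths will be assumed to be cardiovascular in nature unless a non-cardiovascular cause can be clearly shown". That sentence goes on to exclude deaths with no additional information. It is also a definition for CEC adjudication, not a reporting rule for sites. The documents give no expected share of cardiovascular deaths.
- A reader might put the number at 3 to 6 deaths by assuming 0.5-1% mortality (600 × 0.005 = 3; 600 × 0.01 = 6). The documents give no such rate, and the product would be all deaths, not those in conflict.

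**Conclusion.** The contradiction is real and lies in the current text. It covers cardiovascular deaths not due to bleeding; the unassigned unknown-cause deaths and the doubly assigned hemorrhagic deaths are defects of the same section. The consequence is a possible delay in the sponsor's causality and expectedness assessment, including for a drug reaction first taken for a cardiac event. The contrast is a firm 24 hours against an eCRF entry with no hour limit. Neither the length of that delay nor the number of deaths can be derived from the documents.

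The conclusion assumes that a site applies Section 6.7.2.2.10 as written, and that the DSMB and CEC charters, which are not part of these documents, do not resolve the conflict. It does not rest on any mortality rate or on the presumption of cardiovascular death. The point is modest in scope but concerns a subject-safety reporting rule and is cheap to correct.

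**What to change.** Reconcile Sections 6.6.1, 6.7.2.2.6 and 6.7.2.2.10. Limit the exception in Section 6.7.2.2.10, and its restatement in Section 6.6.1, to non-fatal endpoint events, so that every death goes to the sponsor within 24 hours as Section 6.7.2.2.6 already states. Add a cross-reference between the two reporting sections. This also removes the gap for unknown-cause deaths and the overlap for cardiovascular hemorrhage, since cause would no longer decide whether a death is reported promptly.

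Leave the regulatory duties in Section 6.7.2.2.5 unchanged. The amendment should not add an exemption of cardiovascular deaths from regulatory submission: the 7-day duty for fatal unexpected suspected reactions has no carve-out for endpoint events, and such a sentence would create a new conflict.

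The cost is protocol wording, a memo to the sites and a few extra 24-hour reports. Endpoint adjudication, DSMB review and the analysis are unaffected.

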6.7.2.2.7 Reporting of Pregnancies

Pre-clinical genotoxicity studies with PZ-128 were negative and the reproductive and developmental risk of PZ-128 is likely low. However, reproductive and teratogenicity studies have not been performed and therefore the risks to the human embryo or fetus or sperm are unknown at this time. Women of child-bearing potential recruited into the study must have a negative urine pregnancy test (urine beta-HCG) prior to randomization and within 24 hours of treatment with the study drug. Women of child-bearing potential must agree to use a medically accepted method of contraception during the study from the time of providing written informed consent through 90 days after dosing with the study drug and will undergo a post study drug infusion pregnancy test (urine beta-HCG) at the 14-day Follow-Up Visit. If a female subject becomes pregnant or suspects she is pregnant while participating in this study, she must inform her treating obstetrician and principal investigator immediately. Pregnancy information on female clinical study subjects will be collected by the sponsor. If a female subject becomes pregnant during the course of the study, the study drug must be discontinued (if not already administered) and the investigator or qualified designee must contact the sponsor within 5 working days of the investigator or qualified designee first becoming aware

of the pregnancy. If a serious adverse event occurs in conjunction with the pregnancy, then the reporting time frame for an SAE (1 working day) and method of reporting must be met. The sponsor's representative will provide instructions on how to collect pregnancy information (i.e., Pregnancy Notification Form) including follow-up data on the outcome of the pregnancy.

Male participants will be advised to use a medically accepted method of contraception during the study from the time of study drug administration through 90 days after dosing with the study drug. Written information will be provided to the participating male subjects at the time of enrollment in the study's informed consent document which may be shared with their female partner(s) as to the unknown risks to a future pregnancy. If a female partner conceives and becomes pregnant while the male subject is participating in this study, the sponsor should be notified as per the procedures described above. However, information about the pregnancy may only be collected by the investigator and released to the sponsor if the female partner of the male subject provides written consent to release such information via an IRB-approved authorization/ consent form. A female partner of a male subject should only be presented with the authorization/consent form if a pregnancy or suspected pregnancy occurs. The sponsor will provide clinical sites with templates for these related documents to use as a model and the local IRB guidelines and approval process will be adhered to.

6.7.2.2.8 Preplanned Hospitalizations or Procedures

Hospitalization for SAE reporting purposes is defined as an inpatient hospital stay equal to or greater than 24 hours. Emergency room visits that do not result in admission to the hospital should be evaluated for one of the other "serious" outcomes.

Hospitalization admissions and/or surgical procedures/operations scheduled to occur during the entire study period, but planned prior to study enrollment/randomization are not considered AEs if the illness or disease existed before the subject was enrolled/randomized in the trial, provided that it did not deteriorate in an unexpected manner during the trial (e.g., surgery performed earlier than planned). If the event/condition worsens during the study, however, it must be reported as an AE (or SAE, if the event/condition results in a "serious" outcome).

As per the exclusion criteria (**Section 6.3.2**), major surgical procedures should not be planned to take place within 30 days following the study drug administration/catheterization/PCI.

